Statistical Methods (continued)	
Secondary Endpoints
 
• Change in Hb and clinical measures of hemolysis (unconjugated bilirubin, % reticulocyte, absolute reticulocyte, and lactate dehydrogenase [LDH]) from Baseline• Proportion of participants with an Hb increase > 1 g/dL compared to Baseline• Incidence rate of VOCs 
Exploratory Endpoints
 
• P50 and P20 at 8 hours and 24 hours postdose• PK of voxelotor as assessed by population PK analysis using nonlinear mixed-effect modeling• % Hb occupancy at 8 hours and 24 hours postdose• CGI-C• PGI-C 
Sample Size
 
As this is an exploratory study to provide descriptive information on the tolerability, safety and efficacy of voxelotor at dose levels > 1500 mg daily, the sample size chosen was based on previous experience in exploratory studies to support the assessment of a MTD based on descriptive summaries of safety and PK data. The sample size of up to 40 participants takes into account the differential tolerance in participants, some potentially tolerating 3000 mg daily, while others only tolerating lower dose levels. An effort will be made to enroll a number of subjects sufficient to ensure that at least 6 participants are treated at the study level MTD.
 
Populations for Analysis
 
Safety Population: All participants who receive at least one dose of study drug will be included in the safety population.
 
PK Population: The PK population will consist of all participants who receive any amount of study drug and have at least one measured concentration at a scheduled PK time point after the start of dosing.
 
Analyses
 
TEAEs, defined as events that occur on or after Day 1 of study drug or the worsening of a pre-existing condition on or after Day 1 of study drug, will be classified according to the Medical Dictionary for Regulatory Activities (MedDRA). The incidence of TEAEs and relatedness to study drug, as assessed by the Investigator, will be summarized descriptively by maximum dose level tolerated.
 
Clinical laboratory tests, ECGs, and vital signs over time will be summarized by maximum dose level tolerated using descriptive statistics.
 
An Hb responder endpoint, defined as an increase in Hb of > 1 g/dL compared to Baseline, will be summarized. Additionally, change from baseline in Hb and clinical measures of hemolysis (unconjugated bilirubin, % reticulocyte, absolute reticulocyte, and LDH) will be summarized by maximum dose level tolerated using descriptive statistics.
 
The incidence of VOCs will be summarized by maximum dose tolerated.

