1.5.1. Study Rationale

In the pivotal Phase 3 Study GBT440-031, voxelotor was shown to have a dose-dependent (1500 mg > 900 mg orally daily), and clinically meaningful increase in Hb, as well as concurrent reductions in clinical measures of hemolysis. Study GBT440-029, is designed to assess tolerability, safety, and PD of voxelotor dose levels higher than 1500 mg daily (the maximum dose in the pivotal Phase 3 study) and to compare these results to the 1500 mg dose. The rationale for this study is based on an exposure-response analysis from the pivotal Study GBT440-031, which showed a linear relationship between whole blood voxelotor and %Hb occupancy and efficacy as measured by improvement in Hb (see Figure 1 below) and hemolysis markers. The 1500 mg dose led to a mean Hb occupancy of 29% and led to a mean Hb increase of 1.1 g/dL. At 3000 mg of voxelotor, assuming a linear relationship, the mean Hb occupancy is projected to be 49.3% with a Hb increase of 2.04 g/dL. Furthermore, no dose level has been associated with exposure-related concerning safety signals, and a maximum tolerated dose (MTD) has not been defined. Treatment-related AEs were mostly grade 1/grade 2 gastrointestinal events. Given the predicted improved efficacy of higher doses, and lack of dose-limiting safety concerns, this study will investigate the potential for a greater benefit/risk for higher doses in patients with SCD.

In this study, baseline response will be characterized in participants receiving a 3-week treatment regimen with voxelotor 1500 mg and compared, within and across participants, to the response with the highest dose level tolerated at steady state. Dose escalation will be done in 3-week increments to assess tolerability at the escalated dose.

Figure 1: Relationships Between Change from Baseline in Hemoglobin at Week 24 and Percent Hemoglobin Occupancy

pkpd-wk24-hgb-20190508.pdf

C_{min} , minimum plasma concentration at steady state; CFB, change from baseline; Hb, hemoglobin.

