2.1. Primary Objective

- To evaluate the tolerability and safety of voxelotor at daily doses of > 1500 mg (2000 mg to 3000 mg) in participants with SCD

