10. DATA ANALYSIS AND STATISTICAL PLANS

10.1. Endpoints

10.1.1. Primary Endpoint

The primary endpoints are:

- TEAEs and SAEs

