10.2. Determination of Sample Size

As this is an exploratory study to provide descriptive information on the tolerability, safety, and efficacy of voxelotor at dose levels > 1500 mg daily, the sample size chosen was based on previous experience in exploratory studies to support the assessment of a MTD based on descriptive summaries of safety and PK data. The sample size of up to 40 participants takes into account the differential tolerance in participants, some potentially tolerating 3000 mg daily, while others only tolerating lower dose levels. An effort will be made to enroll a number of subjects sufficient to ensure that at least 6 participants are treated at the study level MTD.

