10.3. Populations for Analysis

Safety Population: All participants who receive at least one dose of study drug will be included in the safety population.

Pharmacokinetic Population: The PK population will consist of all participants who receive any amount of study drug and have at least one measured concentration at a scheduled PK time point after the start of dosing.

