10.4. Data Analysis

Data will be presented by maximum dose level.

A TEAE, defined as an event that occurs on or after Day 1 of study drug or the worsening of a pre-existing condition on or after Day 1 of study drug, will be classified according to the Medical Dictionary for Regulatory Activities (MedDRA). The incidence of TEAEs and relatedness to study drug, as assessed by the Investigator, will be summarized descriptively by maximum dose level tolerated.

Clinical laboratory tests, ECGs, and vital signs over time will be summarized by maximum dose level tolerated using descriptive statistics. Change from baseline in ECG intervals will be evaluated using descriptive statistics. If an effect on mean change from baseline in QTc interval exceeding 10 msec is observed, concentration-QTc analysis may be explored. Results from the diagnostic interpretation will be summarized by maximum dose tolerated.

An Hb responder endpoint, defined as an increase in Hb of > 1 g/dL compared to Baseline, will be summarized. Additionally, change from baseline in hemoglobin and clinical measures of hemolysis (unconjugated bilirubin, % reticulocyte, absolute reticulocyte, and LDH) will be summarized by maximum dose level tolerated using descriptive statistics.

The incidence of VOCs will be summarized by maximum dose tolerated.

The CGI-C and PGI-C will be summarized by maximum dose level tolerated.

Population PK analysis using nonlinear mixed-effect modeling will be performed to characterize voxelotor PK in plasma, and whole blood.

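### TEAEs, the primary endpoint, are summarised only by maximum dose level tolerated, so events behind a lasting step-down in escalation are reported under a lower dose than the one taken at onset

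*Combined protocol and SAP*

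**What the plan says.** Section 10.1.1 names "TEAEs and SAEs" as the primary endpoints. Section 2.1 sets the primary objective as tolerability and safety at daily doses from 2000 to 3000 mg.

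Section 10.4 opens with "Data will be presented by maximum dose level" and then gives the rule for adverse events: "The incidence of TEAEs and relatedness to study drug, as assessed by the Investigator, will be summarized descriptively by maximum dose level tolerated". The synopsis repeats that TEAEs "will be summarized descriptively by maximum dose level tolerated". I found no planned summary of TEAEs or SAEs by dose at onset, by period or by dose received.

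Under Section 3.2, participants take 1500, 2000, 2500 and 3000 mg per day in successive 3-week periods. If a level above 1500 mg is not tolerated in escalation, the participant may go back to a previous level, which is then given for the 24-week observation period. Appendix B (footnote i) confirms that observation is at the maximum tolerated dose or 3000 mg. On who is analysed, Section 10.3 says: "All participants who receive at least one dose of study drug will be included in the safety population".

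**The concern.** The column in which a participant's events appear is decided by whether those events were tolerated. Someone who fails 3000 mg and continues at 2500 mg is tabulated at 2500 mg, together with the events that forced the reduction. The 3000 mg column then holds no participant who entered observation at a lower dose after failing 3000 mg.

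Two stated purposes depend on knowing what happened at which dose. Section 1.5.1 wants to study the higher doses "and to compare these results to the 1500 mg dose", and Section 10.2 wants the sample to "support the assessment of a MTD based on descriptive summaries of safety and PK data". An MTD judgement needs the events that occurred at the dose that failed. Column sizes show how many participants ended at each level, but not which events stopped them. Nor do they separate step-downs for toxicity from a halt to escalation recommended by the Safety Monitoring Committee (SMC).

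The columns may also fail to cover everyone. No rule places a participant who stops during escalation, and someone who stops because 1500 mg is not tolerated has no tolerated level at all.

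**Working it through.** The plan states no figure to reproduce: the sample of up to 40 is not derived from rates, power or precision. The check traces the grouping rule through the design and then counts nominal weeks.

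**Inputs (Section 3.2).** Four escalation periods of 3 weeks each (±3 days) at 1500, 2000, 2500 and 3000 mg, then 24 weeks of observation at the maximum tolerated dose or 3000 mg. I assume a one-level step-down, and I count the failed period at its full 3 weeks, so those weeks are upper limits.

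**Where an event goes under Section 10.4.**
- Onset at 3000 mg, lasting step-down to 2500 mg: reported under 2500 mg.
- Onset at 2500 mg, lasting step-down to 2000 mg: reported under 2000 mg.
- Onset at 2000 mg, lasting step-down to 1500 mg: reported under 1500 mg.
- Onset at 1500, 2000 or 2500 mg in a participant who later keeps 3000 mg: reported under 3000 mg.
- Onset at 3000 mg, temporary reduction or hold, then back to 3000 mg: reported under 3000 mg, so not shifted.

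**Nominal weeks by path.** The label matches the dose taken for 3 + 24 = 27 weeks on every path.

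| Path | Column | Total weeks | Label matches dose | Higher dose reported lower | Lower dose reported higher |
|---|---|---|---|---|---|
| Keeps 3000 mg | 3000 | 3+3+3+(3+24) = 36 | 27/36 = 75.0% | 0 | 9/36 = 25.0% |
| 3000 to 2500 mg | 2500 | 3+3+(3+24)+3 = 36 | 27/36 = 75.0% | 3/36 = 8.3% | 6/36 = 16.7% |
| 2500 to 2000 mg | 2000 | 3+(3+24)+3 = 33 | 27/33 = 81.8% | 3/33 = 9.1% | 3/33 = 9.1% |
| 2000 to 1500 mg | 1500 | (3+24)+3 = 30 | 27/30 = 90.0% | 3/30 = 10.0% | 0 |

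In the last row, the 3 weeks at 2000 mg are all of that participant's exposure above 1500 mg (3/3 = 100%). None of it appears in a column within the primary objective's range.

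**Direction.** For events that cause a lasting step-down, the shift is always downward. For all TEAEs together there is also an upward shift (last column), and the documents give no event rates with which to weigh the two.

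**Denominator.** A completed level lasts 3 weeks if it is passed through and 27 if it is kept, a ratio of 27/3 = 9. A table by onset dose therefore needs exposure time as well as participant counts.

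**The case against.** The strongest reply is that grouping by maximum dose tolerated is deliberate. Section 1.5.1 describes comparing response at 1500 mg with response at the highest level tolerated, and Section 10.2 explains the sample size by differing tolerance. The spread of participants across these columns is itself a tolerability result, and the label matches the dose taken for 75% to 90% of nominal weeks. This stands as a reason to keep the table. It does not make the table sufficient, because the Section 1.5.1 wording concerns response, and the events that define intolerance fall in the weeks where the label does not match.

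A second reply is that dose-specific safety is watched during the study: Section 3.7.2 counts related SAEs at a given dose level, and the SMC reviews all safety data (Section 3.4). That covers conduct, not the reported primary result.

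Third, the opening sentence of Section 10.4 omits the word tolerated and could mean maximum dose received. The specific TEAE sentence and the synopsis both say tolerated. On the other reading, step-down events would sit under the higher dose, but events at lower doses would still be reported under it as well.

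Fourth, the study is descriptive, and the missing table could be built later from dosing records. That is true and limits the severity; such a table would then not be pre-specified.

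A reader might go further and infer that every event leading to a reduction is moved to a lower dose. The documents do not support this. Section 3.7.3.1 allows for temporary reductions, and Appendix C lets participants return to the dose they were taking, in which case the event keeps its column.

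**Conclusion.** The point holds for lasting step-downs during escalation. Followed as written, the only specified summary of the primary endpoint reports the events behind them under a lower dose than the one taken, and reports lower-dose events under 3000 mg for those who keep it (9 of 36 nominal weeks). It therefore cannot show safety dose by dose from 2000 to 3000 mg, which is the primary objective.

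The size is given in weeks, not events. It rests on the nominal schedule, one-level step-downs and reading the label as maximum dose tolerated. The documents give no toxicity or step-down rate, so the number of events or participants affected is not estimated.

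A reader might also infer that the plan makes 3000 mg look safer overall. That is not established, because the upward and downward shifts work against each other. Nor does the absence of lasting escalation step-downs from the 3000 mg column measure anything: it follows from how the group is defined. The change should be made before analysis; no data are lost without it.

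**What to change.** Keep the table by maximum dose level tolerated and change Section 10.4 in two ways.

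1. **Add a TEAE and SAE summary by dose level at onset.** Use the level taken on the onset date or, during a hold or after the last dose, the last level taken. Use the number of participants exposed at each level as denominator, and show person-weeks at each level. Flag events that led to a hold, reduction or discontinuation.
2. **Define the groups of the existing table.** Use the level assigned at the start of observation, and state that the opening sentence means the same thing. Put participants who stop during escalation in a separate 'stopped during escalation' column, so that the columns sum to the Safety Population. This avoids deriving a label from dose-limiting toxicities, whose list in Section 3.7.3.1 is open-ended. A dose change during observation would not move a participant between groups; it would show in the new table.

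The cost is a short derivation paragraph and one extra set of tables, with no new visits or samples. AE duration (Section 9.2.1) and treatment administration (Section 11.2) are already recorded. The minimum AE details in Section 9.2.1 do not list action taken, so check that the CRF captures it for the flag.

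The new table has limits: events soon after a dose change may belong to the earlier level, and dose is confounded with time on drug. It should stay descriptive.

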3.2. Study Design

This is an open-label, sequential period, within-participant dose escalation study. Up to 40 participants with SCD (HbSS or HbSB⁰) who are 18 to $<$ 60 years of age, inclusive, will be enrolled.

Study participants will undergo up to four periods of voxelotor administration at progressively higher dose levels from 1500 mg until either a MTD or 3000 mg daily dose is reached, whichever occurs first ([Figure 2](#)):

- Period 1: 1500 mg per day: 1500 mg once daily (3×500 mg tablets) for 3 weeks (± 3 days)
- Period 2: 2000 mg per day: 1000 mg (2×500 mg) BID for 3 weeks (± 3 days)
- Period 3: 2500 mg per day: 1500 mg (3×500 mg) in morning and 1000 mg (2×500 mg) in evening daily for 3 weeks (± 3 days)
- Period 4: 3000 mg per day: 1500 mg (3×500 mg) BID for 3 weeks (± 3 days)
- Observation Period: MTD or 3000 mg daily for 24 weeks
- Safety Follow-up Period: from day of last dose to 28 days postdose.

[figure not shown]
If at any time a dose level $>$ 1500 mg is not tolerated by a participant in the dose escalation period, the dose may be reduced to a previous level for the participant, which will then be administered for 24 additional consecutive weeks as an observation period. Dose modifications are allowed during the observation period in consultation with the Sponsor's Medical Monitor ([Appendix C](#)).

If 1500 mg daily is the MTD for a participant, then the participant may enter the observation period and continue to receive 1500 mg, for up to 24 weeks or until they are able to roll over into the open-label extension or receive commercial voxelotor, where available. If the participant discontinues early from the study, the participant will undergo an End of Study (EOS) visit approximately 28 days after the last dose and will not be eligible for the open-label extension study.

The safety of study participants will be closely monitored by the study team. In addition, a Safety Monitoring Committee (SMC) will review safety, tolerability, and available PK and PD data at regular intervals (Section [3.4](#)). Blood draws for PK and PD (including Hb and hemolysis markers), routine chemistry and hematology laboratory tests, and 12-lead ECGs in triplicate will be obtained periodically, as listed in the Schedule of Assessments ([Appendix A](#), [Appendix B](#)).

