3.4. Safety Monitoring Committee

The SMC will closely monitor the safety of the study participants throughout the duration of study. The SMC will review the totality of safety, tolerability, and available PK and PD data to monitor safety.

The SMC will be composed of the Principal Investigator or designee and Sponsor representatives, including the Study Director/Medical Monitor, Clinician with disease expertise, Biostatistician, and Safety Scientist. Details of the scope, responsibilities, and frequency of the SMC will be provided in the SMC Charter.

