8.7. Electrocardiograms

Electrocardiograms (12-lead) will be recorded after 10 minutes of rest in the supine position. ECGs recorded at Screening, on Days 1 and 7 of each period, and Day 21 in Period 4 will be recorded in triplicate for evaluation at a central ECG laboratory (refer to the Schedule of Assessments, [Appendix A](#), [Appendix B](#)). Other ECGs will be recorded as singles.

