8.13.5. Pharmacokinetic Sample Collection

Blood samples for whole blood and plasma PK assessments will be collected according to the Schedule of Assessments ([Appendix A](#), [Appendix B](#)). Whole blood and plasma concentrations of voxelotor will be measured using a validated liquid chromatography mass spectrometry (LCMS) assay.

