8.18. Order of Assessments

Visits should take place in the morning. Participants are instructed to hold study drug until a predose blood sample for PK is obtained at the investigational site.

For procedures scheduled to be performed at the same timepoint, the order of assessments is as follows: vital signs, PK sample collection, blood draw for PD/safety laboratory assessments, ECGs. If times are delayed due to technical difficulties, this will be noted but not considered a protocol violation.

The predose PK sample should be collected within 30 min prior to dosing.

On Day 1 in Period 1:

- Triplicate ECGs should be recorded at 3 timepoints prior to dosing (-45 min, -30 min, -15 min).
- Postdose triplicate ECGs (after the morning dose) should be recorded within 15 min following the 2-hour PK sample collection.

On Day 1 in Periods 2, 3, and 4, on Day 7 in all periods, and on Day 21 in Period 4:

- Predose triplicate ECGs should be recorded within 15 min following the predose PK sample collection.
- Postdose triplicate ECGs (after the morning dose) should be recorded within 15 min following the 2-hour PK sample collection.

All PD assessments should be performed after the PK assessments. RBC deformability and dense cells will be tested, if feasible, by the local or collaborating lab at the time of collection.

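### QTc change is tabulated by highest tolerated dose without confidence limits, and the concentration-QTc model is optional behind an undefined 10 msec trigger: a cheap reporting improvement

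*Combined protocol and SAP*

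**What the plan says.** Section 10.4 (Data Analysis) gives the default ECG summary: "Clinical laboratory tests, ECGs, and vital signs over time will be summarized by maximum dose level tolerated using descriptive statistics". It then says that changes in ECG intervals will be described, without naming a grouping or a confidence interval, and adds the only QT model: "If an effect on mean change from baseline in QTc interval exceeding 10 msec is observed, concentration-QTc analysis may be explored". The section does not name the QT correction. QTcF appears only in the abbreviations and in exclusion criterion 12.

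Data collection carries no such condition. Under Section 8.7, ECGs at Screening, on Days 1 and 7 of each period and on Day 21 of Period 4 "will be recorded in triplicate for evaluation at a central ECG laboratory". Section 8.18 ties them to PK sampling: "Postdose triplicate ECGs (after the morning dose) should be recorded within 15 min following the 2-hour PK sample collection". From Period 1 Day 7 onward, predose triplicates likewise follow the predose PK sample within 15 minutes. Appendix A footnote c has every triplicate read centrally.

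Section 1.5.1 says the study will assess doses above 1500 mg "and to compare these results to the 1500 mg dose". Section 3.2 provides that, when a dose is not tolerated, "the dose may be reduced to a previous level for the participant, which will then be administered for 24 additional consecutive weeks".

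**The concern.** The primary objective is safety and tolerability above 1500 mg a day. For QTc a reader will ask two things: how large the change was on each dose, and how precisely it is known.

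The planned column answers a different question. It classifies participants by what they eventually tolerated, so an ECG recorded on a dose that was not tolerated is filed under a lower one. Without interval estimates, a mean just under 10 msec could be taken as reassuring at group sizes where it says little. The paired ECG and PK data are collected in every case, but their use is left to a discretionary decision after the means have been seen, against a threshold that can be read in several ways.

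**Working it through.** **There is no plan figure to reproduce.** Section 10.2 bases the sample size on experience and gives no SD. Two of its numbers are used here: up to 40 participants, and an aim of at least 6 at the study-level MTD. The SD of QTc change is an assumption: 8, 12 or 16 msec.

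**1. Column versus dose taken.** Take a participant reduced from 2500 to 2000 mg during Period 3, after the Day 7 visit. Count post-baseline triplicate time points through Period 3 Day 7 by the dose last taken (Sections 8.7 and 8.18):

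- 1500 mg: Period 1 Day 1 at 2 h, Period 1 Day 7 predose and 2 h, Period 2 Day 1 predose = 4
- 2000 mg: Period 2 Day 1 at 2 h, Period 2 Day 7 predose and 2 h, Period 3 Day 1 predose = 4
- 2500 mg: Period 3 Day 1 at 2 h, Period 3 Day 7 predose and 2 h = 3

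The total is 4 + 4 + 3 = 11. If columns are the highest dose tolerated, all 11 sit under 2000 mg, although only 4 followed that dose. Appendix B footnote b then requires a further visit with the Day 21 assessments, so 11 is not the participant's full count. Day 1 predose ECGs in Periods 2 to 4 carry the new period's label but follow the previous dose.

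**2. What a mean near the trigger shows.** Upper two-sided 90% limit = mean + t(0.95, n-1) × SD/√n, with t = 2.015 at n=6 and 1.685 at n=40.

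| | SD 8 | SD 12 | SD 16 |
|---|---|---|---|
| n=6: half-width | 6.6 | 9.9 | 13.2 |
| n=6: upper limit for mean 9.9 | 16.5 | 19.8 | 23.1 |
| n=6: mean at which the upper limit equals 10 | 3.4 | 0.1 | -3.2 |
| n=40: half-width | 2.1 | 3.2 | 4.3 |
| n=40: upper limit for mean 9.9 | 12.0 | 13.1 | 14.2 |
| n=40: mean at which the upper limit equals 10 | 7.9 | 6.8 | 5.7 |

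**3. Precision lost by splitting.** Suppose 40 participants take 1500 mg and divide evenly over four tolerated-dose columns (assumed). Each Period 1 cell then has n=10, with t(0.95, 9) = 1.833. The half-width is 1.833 × 8/√10 = 4.6 to 1.833 × 16/√10 = 9.3 msec per column, against 2.1-4.3 msec for all 40 by dose taken.

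**4. The undefined trigger.** Purely as an illustration, let the change be proportional to dose and 12 msec at 3000 mg. The four dose levels then have means of 6, 8, 10 and 12 msec, and their average is (6 + 8 + 10 + 12)/4 = 9.0 msec. The same data cross 10 msec at the top dose but not when pooled over periods, and the wording does not say which mean counts.

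**The case against.** The strongest reply is that this is an exploratory, uncontrolled study, that QTc is not a named endpoint, and that the tables are more informative than their headings suggest. Much of that stands.

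- ECGs are summarised over time, and during escalation the period largely fixes the dose. If n and mean are tabulated by visit, weighting across columns recovers the by-dose mean. A reader might infer that the plan hides QTc change at the doses taken; the text does not support that. What is missing is the pooled summary with its precision, and correct assignment of the Day 1 predose ECGs.
- Section 1.5.1 goes on to describe the comparison as 1500 mg against each participant's highest tolerated dose. A tolerated-dose column with period rows suits that contrast, so the grouping does not contradict the rationale.
- Section 10.4 refers both to maximum dose level and to maximum dose level tolerated. If the maximum dose level defines the column, the example participant could be placed under 2500 mg. The column would still not be the dose taken for 8 of the 11 points.
- Descriptive statistics can include confidence intervals, and a model that may be explored above 10 msec is not forbidden below it. Section 3.4 adds: "The SMC will review the totality of safety, tolerability, and available PK and PD data to monitor safety". A reader might turn the trigger into a rate of missed QT signals. That is not supported, because summaries and review continue either way. Nor can a chance of crossing the trigger be stated for the plan while it leaves open which means count.

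The reply does not remove the point that an unconditional analysis costs little once PK-timed, centrally read triplicates have been collected.

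**Conclusion.** The point holds as a worthwhile, inexpensive improvement in precision and by-dose reporting. That the column is not the dose taken, that no confidence limit is named and that the trigger is undefined all follow from the text and need no assumption. The sizes do rest on assumptions. With an SD of 8-16 msec, a mean of 9.9 msec is compatible with a change of up to 17-23 msec at n=6 and 12-14 msec at n=40. With an even four-way split, the half-width at 1500 mg is a little over twice as wide per column as by dose taken.

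It would be tempting to say that adding the limits and the model would let the study rule out a 10 msec drug effect. It would not. There is no placebo correction, everyone escalates in the same order, so concentration is partly confounded with calendar time, and ECGs paired only at predose and 2 h may miss the daily peak.

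**What to change.** 1. Keep the planned tables and add one: change in QTcF from the Period 1 Day 1 predose triplicates, with two-sided 90% confidence intervals, by dose level last taken before the ECG and by time point (predose, 2 h). Count Day 1 predose ECGs in Periods 2 to 4 with the previous dose level.
2. Replace the trigger sentence with a supportive concentration-QTcF mixed model fitted to all paired triplicate ECG/PK data regardless of observed means, with participant random effects, a linearity check and a sensitivity analysis with a period or time term. Report predicted change with a 90% interval at the observed 2-hour concentration for each dose level. Name the primary matrix in advance, because Section 8.13.5 provides for two: "Blood samples for whole blood and plasma PK assessments will be collected according to the Schedule of Assessments".
3. State that the bounds are not placebo-corrected, that concentration is partly confounded with calendar time and that the daily peak may be missed, so that they describe change from baseline and do not exclude a drug effect.

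Separately, reconcile Appendix A footnote j, which gives no PK times for Period 4 Day 21, with footnote c and Section 8.18, which time that day's ECGs by predose and 2-hour PK samples.

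The cost is one extra table and one extra model, with no additional ECGs, samples or participants.
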